10.3.3.2. Laboratory Tests

Laboratory values as well as changes and percent changes from baseline at each time point will be summarized. Analyses will also be performed for each laboratory parameter on incidence rates of potentially clinical significant (PCS) values for patients without PCS value at baseline.

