### 11.2.1. Laboratory normalization

Because values of laboratory parameters in this study are provided from different local laboratories with different units and normal ranges, all numerical laboratory values will be converted to the conventional units and normalized to a standard set of reference/normal ranges [Chuang-Stein, 1992 and 2001]. The normalization process will be performed for each of the laboratory parameters. The method was adapted by a scale model described in Karvanen [2003] for values outside the normal local range and in the case of only one-sided defined standardized normal ranges. Details of the standardization process are described in the Appendix (Section 20.2). Normalized laboratory values will be used for the analyses of summary statistics, including relative and percent changes from baseline, described in Section 11.2.2.

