### 20.2. LABORATORY NORMALIZATION

Because values of laboratory parameters are provided from different study centers with different local laboratories, and with inconsistent units and normal ranges, all numerical laboratory values will be converted to conventional units and normalized to a standard set of reference/normal ranges by a location-scale model as described by Chuang-Stein (1992 and 2001). The method was adapted by a scale model described in Karvanen [2003] for values outside normal local range and in the case of only one-sided defined standardized normal ranges.

The normalization process will be performed for each laboratory parameter.

For numerical laboratory values, the normalized values will be proportional to the ratio of the widths of reference ranges and aligned with the corresponding lower limits. For example, let  $(L_S, U_S)$  denote the standard reference range. Let  $\varphi$  denote the laboratory value provided from Laboratory A, which is to be normalized. The normalized value,  $\varphi_S$ , can be derived from the formula,

$$\varphi_S = L_S + \beta \times (\varphi - L_A),$$

where (LA, UA) represents the reference range from Laboratory A and  $\beta$  denotes the ratio of the width from standard reference range over the width from Laboratory A (ie,  $\beta = (US - LS) / (UA - LA)$ ).

If one, say the lower, of the limits of a reference range is missing then the missing limit will be imputed according to the ratio of the limits from one of the closest reference ranges provided in this study. For example, let LM denote the missing lower limits from Laboratory M. Its corresponding higher limit, UM, is found to be closest to the upper limit, UC from Laboratory C among all the reference upper limits in the study. Then, LM will be imputed by the formula,

$$L_M = L_C \times (U_M / U_C),$$

where LC denotes the lower limit from Laboratory C. For cases where only the upper local limits are missing (i.e., the lower ones are not missing), the same imputation process will be performed. For cases where both limits of a local reference range are missing, the missing upper and lower limits will be imputed by the largest upper and lowest lower limit among all the observed local reference ranges, respectively.

For laboratory parameters with one-sided standard reference ranges the scale normalization formula (see formula 21 in Karvanen, 2003) will be applied as follows:

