Let  $L_S$  and  $U_S$  denote either side of the standard reference range.

Let w,  $L_w$  and  $U_w$  denote the value and either side of the local reference range.

If only  $L_S$  is available the normalized value will equal w \*  $L_S / L_w$ .

If only  $U_S$  is available the normalized value will equal w \*  $U_S / U_w$ .

For values outside the local reference ranges, the same formula will be applied to avoid complications by negative normalized values using the notation above:

If w is below  $L_w$ , then the normalized value will equal w \*  $L_S / L_w$ .

If w is above  $U_w$ , then the normalized value will equal w \*  $U_S / U_w$ .

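### SAP 11.2.1 takes laboratory percent change from baseline on location-scale-normalised values, which distorts it for two-sided ranges unless the local and standard limits are proportional

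*SAP*

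**What the plan says.** Protocol 10.3.3.2 plans: "Laboratory values as well as changes and percent changes from baseline at each time point will be summarized". It does not mention normalisation.

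SAP 11.2.1 says that all numerical laboratory values will be unit-converted and "normalized to a standard set of reference/normal ranges", because local laboratories use different units and normal ranges. It continues: "Normalized laboratory values will be used for the analyses of summary statistics, including relative and percent changes from baseline". SAP 11.2.2 then plans these change summaries by time point.

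SAP 20.2 gives the algorithm, in which:

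- values are "normalized to a standard set of reference/normal ranges by a location-scale model";
- "the normalized values will be proportional to the ratio of the widths of reference ranges and aligned with the corresponding lower limits";
- the multiplier beta "denotes the ratio of the width from standard reference range over the width from Laboratory A".

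There are two exceptions, both pure scaling by a ratio of limits. One begins: "For laboratory parameters with one-sided standard reference ranges the scale normalization formula". The other reads: "For values outside the local reference ranges, the same formula will be applied to avoid complications by negative normalized values".

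Neither document lists any reference limits, and the SAP does not say whether the standard set varies with age. SAP section 18, on changes from the protocol, mentions only vital signs.

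**The concern.** Percent change is a ratio, and a ratio survives multiplication by a constant but not addition of one. Aligning the local lower limit with the standard lower limit adds a constant. The percent change in the tables is then not the percent change the patient had, and the discrepancy depends on which laboratory's range applied.

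Normalisation is offered as the answer to differing units and ranges. Within-patient percent change is already unit-free once units are converted, so it does not need this step.

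Laboratory parameters are part of the safety item among the primary endpoints in Protocol 3.3, and SAP section 4 has all data summarised by age cohort. The cohorts run from preterm newborns to adolescents. If local ranges vary with age and the standard set does not, the distortion would differ between cohorts in tables likely to be read side by side.

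**Working it through.** The plan states no figure on this point, so there is none to reproduce. The formulas come from SAP 20.2. **All reference limits below are assumptions**, and baseline and follow-up are taken to share one local range.

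**Formulas.** Let the local limits be `L_A`, `U_A` and the standard limits `L_S`, `U_S`, with `beta = (U_S - L_S)/(U_A - L_A)`. The normalised value g(x) is:

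- inside the local range: `L_S + beta × (x - L_A)`
- below it: `x × L_S/L_A`
- above it: `x × U_S/U_A`

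**General result.** Write r(x) = g(x)/x. The reported follow-up-to-baseline ratio is the true ratio multiplied by r(follow-up)/r(baseline). Below the range r is constant at `L_S/L_A`, and above it r is constant at `U_S/U_A`. Inside, `r(x) = beta + (L_S - beta × L_A)/x`, which moves steadily from the first constant to the second. It follows that:

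- Percent change is exact for every pair only if `L_S = beta × L_A`, which is the same as `L_A/U_A = L_S/U_S` (proportional limits, including both lower limits zero).
- Otherwise any pair of differing values with at least one strictly inside the range is distorted, as is a pair on opposite sides of it. A pair beyond the same limit is exact.
- If `L_A/U_A < L_S/U_S`, r falls as x rises and increases are understated. If the inequality is reversed, they are overstated.

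When both values are in range, the reported change is `(x1 - x0)/(x0 + c)` with `c = L_S/beta - L_A`.

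**Worked case.** Creatinine-like, local 0.1-0.4, standard 0.6-1.2 mg/dL, 0.2 rising to 0.4:

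- beta = 0.6/0.3 = 2 and c = 0.6/2 - 0.1 = 0.2
- normalised values: 0.6 + 2 × 0.1 = 0.8 and 0.6 + 2 × 0.3 = 1.2
- reported change: 0.2/(0.2 + 0.2) = +50%, against a true +100%

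**Other true doublings**

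| Local | Standard | Raw values | Normalised values | Reported |
|---|---|---|---|---|
| 0.1-0.5 | 0.6-1.2 | 0.1 to 0.2 | 0.60 to 0.75 | +25% |
| 0.2-0.5 | 0.6-1.2 | 0.2 to 0.4 | 0.6 to 1.0 | +66.7% |
| 0.2-0.4 | 0.6-1.2 | 0.2 to 0.4 | 0.6 to 1.2 | +100% (proportional) |
| 0.1-0.4 | 0.6-1.2 | 0.25 to 0.5 | 0.9 to 1.5 | +66.7% (in range to above) |
| 0.1-0.4 | 0.6-1.2 | 0.5 to 1.0 | 1.5 to 3.0 | +100% (both above) |
| 0.1-0.4 | 0.15-0.45 | 0.2 to 0.4 | 0.25 to 0.45 | +80% |
| 0.1-0.4 | 0.2-0.5 | 0.2 to 0.4 | 0.3 to 0.5 | +66.7% |
| 0.2-0.5 | 0.1-0.4 | 0.2 to 0.4 | 0.1 to 0.3 | +200% |

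In the last row `L_A/U_A` = 0.4 exceeds `L_S/U_S` = 0.25, so the error runs upward.

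**Other analytes, again with assumed ranges**

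- BUN, local 3-12, standard 8-20, 5 to 10: beta = 12/9, normalised 10.67 to 17.33, reported +62.5% against +100%.
- LDH, local 170-580, standard 100-200, 300 to 450: beta = 100/410, normalised 131.7 to 168.3, reported about +28% against +50%.
- Potassium, local 3.7-5.9, standard 3.5-5.0, 4.0 to 5.5: beta = 1.5/2.2, normalised 3.70 to 4.73, reported +27.6% against +37.5%.

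**The case against.** The strongest reply is that the reach is limited and unknown. One-sided standard ranges and pairs beyond the same limit keep their percent change, and the SAP does not say which parameters are one-sided. That stands: how many of the 16 chemistry parameters are affected cannot be determined.

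A reader might infer that the SAP will halve creatinine rises in infants, or that a bias by cohort is established. The documents do not support either. The +50% comes from pairing an assumed local range with an assumed, much higher standard range, and nothing says the standard set ignores age. Better-matched standard limits reduce the error (+80% in one case above) but remove it only if the limits are proportional.

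A reader might also infer a jump where a value crosses a limit and the formula changes. There is none. Both formulas give `L_S` at `L_A` and `U_S` at `U_A`, so only the slope changes.

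Nor does the point show that safety flagging fails. Above the local upper limit the scaling is exact, so 3 × local ULN maps to 3 × standard ULN. SAP 11.2.2 puts raw beside standardised values in the PCS listing, and SAP section 4 promises listings of all eCRF data, so true changes stay traceable. The flags do not repair the percent-change tables, however. A rise from 0.2 to 0.4 (normalised 1.2 in the worked case) is far below the 2 mg/dL creatinine criterion and would not enter that listing.

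Finally, if laboratories differed by an additive assay offset, raw percent change would not be strictly comparable either. The documents do not settle this. The reason the SAP gives is differing units and normal ranges, and it cites no measured offset.

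**Conclusion.** The point holds within stated limits. For parameters with two-sided standard ranges, the rule in SAP 11.2.1 misstates a patient's percent change when at least one value is inside the local range and the limits are not proportional. That follows from the SAP's own formulas. The direction depends on the sign of `L_A/U_A - L_S/U_S`.

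The size is illustrative only. Over the creatinine-like ranges tried, a true in-range doubling was reported as about +25% to +200%, with no error for proportional limits. The actual size depends on reference limits that the documents do not give.

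The consequence is confined to descriptive safety summaries. SAP section 4 plans no formal hypothesis testing, Protocol 3.3 does not name percent change as the laboratory endpoint, and the efficacy analyses do not use these values. It should be corrected because the affected tables would otherwise misreport within-patient change and the remedy is nearly free.

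**What to change.** In SAP 11.2.1 and 11.2.2, compute relative and percent change from baseline within patient from unit-converted, un-normalised values. Keep normalised values for pooled level summaries and for the PCS assessment, whose Table 3 limits refer to the standard range. State whether the standard ranges are age-specific and which parameters have one-sided ranges.

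Do not instead scale every value by `U_S/U_A`. That preserves percent change but loses the alignment at the lower limit on which the electrolyte PCS criteria rely. With the assumed potassium ranges, a value at the local lower limit becomes 3.7 × 5.0/5.9 = 3.14, below 0.9 × 3.5 = 3.15, so a locally normal result would be flagged low. The present map sends it to 3.5, with no flag.

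The cost is a few lines of SAP text and simpler programming. No new data are needed.

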### 11.2.2. Laboratory analysis

Descriptive statistics for the values of serum chemistry as well as relative and percent changes from baseline will be summarized by time point: baseline (screening), every 24 hours during study drug administration (or at the termination of study drug infusion if less than the 24 hours timepoint), and at 4 hours after termination of study drug infusion. Values for each hematology parameter will be presented only at screening.

Values of laboratory tests are considered potentially clinically significant (PCS) if they meet the PCS criteria listed in Table 3. The number (percentage) of patients with post-baseline PCS values who do not have PCS values at baseline will be analyzed for the safety population. For calculation of the percentages, the denominator is based on the number of patients with non-PCS baseline values and at least one post-baseline assessment for the laboratory parameter being analyzed. The numerator is based on patients from the denominator who had at least one post-baseline PCS value for the laboratory parameter being analyzed. A supportive listing of patients with all PCS values will be provided including the patient number, age, gender, treatment time. Both raw and standardized pre-baseline, baseline, and post-baseline values and normal ranges will be in the listing, along with the standardized abnormality flag.

Table 3: Criteria for Potentially Clinically Significant Abnormal Laboratory
Tests

Parameter	Low Limit	High Limit					
Serum Chemistry							
Serum Creatinine, mg/dL	_	≥2 mg/dL					
Triglycerides, mg/dL	_	≥300 mg/dL					
Lipase, U/L	_	≥3 × ULN					
Total Cholesterol, mg/dL	_	≥300 mg/dL					
HDL, mg/dL	_	≤20 mg/dL					
LDL, mg/dL	_	≥200 mg/dL					
VLDL, mg/dL	_	≥100 mg/dL					
Alanine Transaminase (ALT/SGPT), U/L	_	≥3 × ULN					
Aspartate Transaminase (AST/SGOT), U/L	_	≥3 × ULN					
Total Bilirubin, mg/dL	_	≥1.5 × ULN					
Lactate Dehydrogenase (LDH)	_	≥3 × ULN					
Blood Urea Nitrogen (BUN), mg/dL	_	≥1.5 × ULN					
Electrolytes	Electrolytes						
Sodium, mg/L	≤0.9 × LLN	≥1.1 × ULN					
Potassium, mg/L	≤0.9 × LLN	≥1.1 × ULN					
Calcium, mg/dL	≤0.9 × LLN	≥1.1 × ULN					
Magnesium	≤0.9 × LLN	≥1.1 × ULN					

LLN: Lower limit of the standard reference (normal) range.

ULN: Upper limit of the standard reference (normal) range.

### 12. PHARMACOKINETIC/PHARMACODYNAMIC ANALYSES

### 12.1. PRIMARY PK ANALYSIS

Blood concentration versus time data will be analyzed using non-compartmental analysis and/or Nonlinear Mixed-Effect Modeling (NONMEM). The following pharmacokinetic parameters will be estimated:

- Maximum observed blood concentration (Cmax)
- Time to reach  $C_{max}(t_{max})$
- Area under the curve of the blood concentration to the last measurable concentration (AUClast)
- Area under the curve of the blood concentration to infinity (AUCinf)
- Terminal rate constant ( $\lambda_z$ ) and its associated half-life ( $t_{1/2}$ )
- Mean residence time (MRT)
- Total clearance (CL).
- Volume of distribution at steady state (Vss)
- Volume of distribution based in the terminal phase (Vz)

All concentration data will be presented descriptively at each time point. Descriptive statistics comprising N, mean, geometric mean, SD, standard error of mean (SEM), median, %CV, minimum and maximum will be presented for the pharmacokinetic variables (half-life, area under curve [AUC], volume of distribution, clearance, etc.) established by sparse population methodology.

All PK and PD analyses will be using the defined PK/PD population.

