If treatment with an IV antihypertensive agent is still required after 96 hours of clevidipine therapy, the patient may be transitioned to an alternative IV antihypertensive agent according to the institutional standard of care.

Rescue therapy with IV antihypertensive treatment will be determined by the principal investigator per the institutional treatment policy. If a patient is receiving rescue therapy with an IV antihypertensive treatment and transition to an oral antihypertensive agent is required, institutional practice must be followed.

Reference Therapy, Dose and Mode of Administration, Batch Number(s): There will be no reference therapy in this trial.

Efficacy Endpoints:

The primary efficacy endpoints of this trial are:

- Median time and dose to attain the initial prespecified target SBP range (minimum of 20 mmHg and a maximum of 40 mmHg apart) during the first 30 minutes of clevidipine infusion
- Percentage of patients achieving the initial prespecified target SBP range during the first 30 minutes of clevidipine infusion

Safety:

Safety of a prolonged infusion of clevidipine (up to 96 hours) will be assessed according to clinical laboratory parameters. Adverse events and serious adverse events (SAEs) will be assessed from time of consent through 7 days following termination of study drug infusion.

Pharmacology:

• Pharmacokinetic variables (half-life, area under the curve [AUC], volume

of distribution, clearance) established by noncompartmental analysis or sparse population methodology

 Pharmacodynamic variables (relationship between change from baseline in SBP vs. blood concentration and infusion rate)

The secondary efficacy endpoints of this trial are:

- The percentage of patients who reach the initial prespecified target SBP range without falling below the lower limit of the prespecified target range during the first 30 minutes of clevidipine infusion
- The percentage of patients in whom the SBP falls below the lower limit of the prespecified target range at any time during the first 30 minutes and at any time during the entire study drug treatment period
- Percent change in SBP from baseline at each time point during the first 30 minutes of clevidipine infusion
- Percent change from baseline in SBP at each hour after the first 30 minutes of clevidipine infusion up to the cessation of infusion
- Percent change from baseline in SBP over the first 12 hours post study drug termination

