3.3. PRIMARY ENDPOINT(S)

The primary endpoint(s) of this trial are:

- Median time and dose to attain the initial prespecified target SBP range (minimum of 20 mmHg and a maximum of 40 mmHg apart) during the first 30 minutes of clevidipine infusion
- Percentage of patients achieving the initial prespecified target SBP range during the first 30 minutes of clevidipine infusion
- Pharmacokinetic variables (half-life, area under the curve [AUC], volume of distribution, clearance) established by sparse population methodology
- Pharmacodynamic variables (relationship between change from baseline in SBP vs. blood concentration and infusion rate)
- Safety of a prolonged infusion of clevidipine (up to 96 hours) assessed according to clinical laboratory parameters, adverse events and serious adverse events (SAEs) will be assessed from time of consent through 7 days following termination of study drug infusion

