10.3.3.4. Pharmacokinetic Parameters

Blood concentration versus time data will be analyzed using non-compartmental analysis and/or Nonlinear Mixed-Effect Modeling (NONMEM). Following pharmacokinetic parameters will be estimated:

- Maximum observed blood concentration (C_{max})
- Time to reach $C_{max}(t_{max})$
- Area under the curve of the blood concentration to the last measurable concentration (AUC_{last})
- Area under the curve of the blood concentration to infinity (AUC_{inf})
- Terminal rate constant (λ_z) and its associated half-life ($t_{1/2}$)
- Mean residence time (MRT)
- Total clearance (CL).
- Volume of distribution at steady state (V_{ss})
- Volume of distribution based in the terminal phase (V_z)

All concentration data will be presented descriptively at each time point. Descriptive statistics comprise N, mean, geometric mean, SD, standard error of mean (SEM), median, percent coefficient of variation (%CV), minimum and maximum will be presented for the

pharmacokinetic variables (half-life, area under the curve [AUC], volume of distribution, clearance, etc.) established by sparse population methodology.

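### If the sparse-population PK values tabulated under SAP 12.1 are post hoc NONMEM estimates, their SD, %CV and SEM are biased low, and the SAP plans no model-based measure of variability or precision

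*SAP*

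**What the plan says.** Protocol 3.3 lists as a primary endpoint: "Pharmacokinetic variables (half-life, area under the curve [AUC], volume of distribution, clearance) established by sparse population methodology". SAP 12.1 first leaves the method open: "Blood concentration versus time data will be analyzed using non-compartmental analysis and/or Nonlinear Mixed-Effect Modeling (NONMEM". The synopsis is also open, with the variables "established by noncompartmental analysis or sparse population methodology". Protocol 2.1 and 7.4.1 name only the sparse population route.

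The summary rule itself is tied to that route. In SAP 12.1 the summaries "will be presented for the pharmacokinetic variables (half-life, area under curve [AUC], volume of distribution, clearance, etc.) established by sparse population methodology". The summaries it names are "Descriptive statistics comprising N, mean, geometric mean, SD, standard error of mean (SEM), median, %CV, minimum and maximum". Protocol 10.3.3.4 prescribes the same set of statistics for the "pharmacokinetic variables (half-life, area under the curve [AUC], volume of distribution, clearance, etc.) established by sparse population methodology".

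Neither document plans to report a model-based typical value with a confidence interval, the model's between-patient variance, or shrinkage. SAP 12.2 adds that the effect of weight, age, sex and other covariates on CL and Vss may be explored.

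**The concern.** N, SD, minimum and maximum can only be computed from one number per patient. A population fit ordinarily supplies that number as the post hoc (empirical Bayes) estimate. This is a compromise between the patient's own data and the population value, and it leans further toward the population value as the patient's data become less informative. The spread of such estimates is narrower than the true spread between children. Their SD divided by √n is also not the standard error of the mean, because all the estimates share the same fitted population parameters.

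The trial is meant to describe pediatric PK in age groups of about 10–20 patients. On this route, children would look more alike, and the averages more precise, than the data support. The distortion would be unequal: least for clearance, most for parameters that rest on few informative samples. Plots of individual CL or Vss against covariates could also have real relationships flattened.

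**Working it through.** **Stated figures.** The documents give no shrinkage, between-patient SD, residual error or PK precision, so there is no PK figure to reproduce. The only stated precision is for the responder percentage. It reproduces: 1.96 × √(0.90 × 0.10/80) = 6.57% (stated 6.6%), and 1.96 × √(0.85 × 0.15/80) = 7.82% (stated 7.8%). It says nothing about PK.

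**Step 1, the rule.** Let ω² be the between-patient variance, and let s be the posterior variance of a patient's parameter divided by ω² (variance shrinkage).

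- Variance of the post hoc estimates = ω²(1 − s), so the SD ratio is √(1 − s).
- True standard error of the mean = ω/√(n(1 − s)), while the SEM from post hoc estimates = ω√(1 − s)/√n. The SEM ratio is therefore 1 − s.

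Simulation with n = 20 and 40,000 replicates:

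| s | SD ratio | SEM ratio | Coverage of mean ± t × SEM |
|---|---|---|---|
| 0.10 | 0.93 | 0.88 | 92% |
| 0.28 | 0.84 | 0.71 | 85% |
| 0.50 | 0.70 | 0.49 | 69% |

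The SAP plans no confidence interval for PK means. The last column only shows how far a reader would be misled by treating the SEM as a standard error. In a parallel simulation, unshrunk (NCA-like) values with 8 samples gave an SD ratio of 1.03–1.06 and an SEM ratio of 1.00.

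**Step 2, illustration for this schedule.**

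- From the documents: half-lives of 0.6–0.8, 2.2–2.3 and 16–22 min, with 3.3–5.7% of AUC in the terminal phase (Protocol 5.1.1; midpoints 0.7, 2.25 and 19 min and 4.5% used); PK sampling times (SAP Table 2), giving 8–9 post-dose samples.
- Assumed: between-patient CV of 30–40% on CL, central volume and terminal-compartment volume; residual error 20–30%; infusion of 30 min or 2 h; 0, 1 or 3 titrations; the split of AUC between the two fast phases.
- Method: first-order posterior covariance (J′J/σ² + Ω⁻¹)⁻¹ in a three-compartment model, carried through to the parameters that SAP 12.1 lists.

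| Parameter | SD understated by | SEM understated by, 1 − (SD ratio)² |
|---|---|---|
| CL | 1–5% | 2–10% |
| Vss | 9–38% | 17–62% |
| Vz | 4–17% | 8–31% |
| Terminal half-life | 4–21% | 8–38% |

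For example, Vss: 1 − 0.91² = 17% and 1 − 0.62² = 62%. For a known dose, AUC to infinity is dose/CL, so its dose-normalised log-scale spread shrinks as CL does.

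**Step 3, dependence on Sample 10.** After a steady-state infusion, the level at time t is about the terminal AUC share × 2^(−t/half-life) of the pre-stop level.

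- At 60 min: 0.033 × 2^(−60/16) = 0.25% to 0.057 × 2^(−60/22) = 0.86%.
- At 90 min, the end of the allowed window: 0.07% to 0.33%.

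If that sample is not quantifiable, the SD of terminal half-life is understated by roughly 55–95% under the same assumptions.

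**Step 4, sensitivity.** A simpler tri-exponential model with wider assumptions (between-patient 20–40%, residual 15–30%) gave SD ratios of 0.87–0.99 for clearance, 0.68–0.97 for volume and 0.72–0.98 for the terminal rate. Without the 60-minute sample, the terminal-rate ratio was 0.04–0.74.

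**The case against.** A reader might infer that the SAP commits to summarising shrunken individual estimates, so that the error bars of all the primary PK variables are too small. The documents do not support that. Post hoc estimates are never named; they are inferred from the list of statistics. NCA is allowed in SAP 12.1, Protocol 10.3.3.4 and the synopsis. Several listed parameters (observed Cmax, tmax, AUClast) are typical NCA output, and NCA values are not shrunk. This stands, and it makes the point conditional. It does not remove the point, because the sentence that orders SD and SEM refers to sparse-population values.

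Eight or nine post-dose samples is fairly rich sampling, and clearance is barely affected. This also stands, although the count is not assured: Sample 3 requires a titration, and Samples 2 and 4 coincide in a patient who is at target by 1.5 minutes.

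The Sample 10 case is a what-if. The documents show no assay limit and no concentrations, so it is not a property of the plan.

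If weight or age enters the model, estimates shrink toward the covariate-predicted value, and only the unexplained part of the spread is understated. With patients from newborn to 17 years, that may be a modest part of the total.

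Finally, the study is descriptive, and no section uses the PK SD or SEM to set doses. Dosing of later cohorts follows DSMB review, and the precision check uses target-range responders. The stake is therefore correct reporting of primary PK variables, not a decision rule inside the trial.

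**Conclusion.** The point holds in conditional form. On the population route, which the summary sentence and Protocol 3.3 name, SD and %CV of post hoc estimates are too small by the factor √(1 − s), and SEM by (1 − s). The plan contains nothing that would show or correct this. On the NCA route there is no such bias.

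The direction is certain given post hoc estimates; the size is not. It rests on assumed between-patient and residual variability and on half-lives that are not pediatric estimates from this trial. Within those assumptions the effect is negligible to small for CL, possibly material for Vss, Vz and terminal half-life, and severe for terminal half-life only if the last sample cannot be quantified. It would be wrong to read the percentages as predictions, or to apply one figure to all parameters.

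This is more than missing detail, because on the named route the stated SD/SEM rule gives the wrong measure of variability and precision. It should be corrected in the SAP.

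**What to change.** In SAP 12.1:

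1. State, for each parameter, which method supplies the tabulated values (NCA, post hoc NONMEM estimates, or direct observation).
2. Where NONMEM is used, base reported variability and precision on the model: typical value per cohort with 95% CI (covariance step or bootstrap), between-patient variability as omega (CV%) with its relative standard error, and shrinkage per parameter.
3. Keep the descriptive table of individual estimates beside these, with a note that its SD and SEM are not the measures of variability or precision.
4. Use individual estimates in covariate plots (SAP 12.2) only for parameters with low shrinkage.
5. Leave the SD/SEM/%CV table as it is for NCA values.

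Record the addition in SAP section 18. Protocol 10.3.3.4 prescribes the descriptive table, so the model output should be added to it, not replace it. Replacement would also leave the NCA route without a summary.

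Cost: SAP wording and slightly more reporting. A NONMEM run already yields typical values, omega and shrinkage, and no new data are needed. Stated variability and uncertainty will become somewhat larger.
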